For aim 1 and sub-aim 1.1, some interviews at the Duke site will be conducted by telephone in order to reduce barriers to enrollment and therefore obtain the most representative sample possible. These phone consents will be scripted (see separate IRB-approved scripts for Aim 1 and sub-aim 1.1), adhering to the same general consent process described above. Phone consents will NOT be performed at UH or MetroHealth sites, because travel is less of a barrier for these clinic populations.

For aim 2, a partial waiver of consent is requested for pre-screening and chart review procedures as described. Once the subject is screened and agrees to enroll, then informed consent will be obtained at the baseline visit. Prior to the baseline visit, in order to streamline data collection for the participant and study staff, the study staff will perform a chart review of the participant's medical history. Medical history obtained from chart review will be verified with the participant on the day of the baseline visit. Our rationale is that we anticipate a low risk for loss of confidentiality during pre-screening and chart review procedures. In addition, waiting to perform the chart review together with the participant on the day of the procedure would considerably lengthen the study visit, which would inconvenience the participant. If, in the rare case that a qualified participant agrees to participate and is scheduled for a baseline visit, but then fails to attend the baseline visit and decides not to reschedule prior to signing informed consent, then any information collected by chart review will be deleted from the study database.

We plan to obtain verbal consent to record the following demographic variables for all persons that agree to be screened in person or by phone, but who ultimately decline to participate: (1) age, (2) sex, (3) gender identity, (4) race/ethnicity. Thus, at the end of the trial, we will be able to document whether those who declined to participate are different demographically than the population of patients who agreed to enroll. This is important to describe the generalizability of our study findings. Verbal consent will be documented in RedCap. Verbal consent will also be obtained and documented for scheduling and documenting participants' baseline visits in participants' Electronic Medical Records at Duke Health.

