Familial Hypercholesterolemia	
DO NOT include the following:	DO NOT include the following:
Low HDL	Pulmonary hypertension
	Intracranial hypertension
	Venous hypertension
	Pre-eclampsia or Maternal Hypertension
	Portal hypertension
	Ocular hypertension

Randomization: Prior to study start, [name] will develop a 1:1 blocked randomization scheme, stratified by site. This randomization scheme will be carried out using the randomization module in RedCap. Participants will be randomized by RedCap at the time of their baseline visit to avoid randomizing participants who have not yet completed consent.

Education control group: Participants assigned to the education group will receive usual care enhanced with general prevention education delivered by the prevention nurse. This active comparator is appropriate because participants have multiple risk factors for ASCVD, and advisory committees for prior studies have recommended this for similar study populations. The prevention educational modules will be delivered at 4 in-person visits (enrollment, 4, 8, and 12 months), and will consist of evidence-based material on diet, exercise, smoking, sexually transmitted infections, and cancer prevention. As recommended by the design teams, control participants will have access to a wide range of educational materials about healthy living, but will not receive additional counseling from the prevention nurse outside of the 4 in-person visits.

All participants in both intervention and education control arms will complete the following study assessments: 1) in-office BP obtained by a trained research assistant blinded to study group using a standardized protocol¹² (0, 4, 8, 12 months); 2) lipid profile (0, 4, 8, 12 months); 3) perceived ASCVD risk survey⁵⁶ (0, 12 months); 4) provider trust and communication survey (0, 12 months). Study visits will be calculated from the date of the baseline enrollment visit in months. Per protocol, study visits must be completed +/- 14 days from the calculated visit date.

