Visits done between 14 and 28 days after the calculated visit date will be considered a protocol deviation. Visits outside of the +28 day window will not be scheduled and that visit will be considered missing for that patient. The fasting lipid panel blood draw will be done at the time of study visit or within a +/- 10 day window. To limit potential bias, participants, their healthcare providers, and the prevention nurse delivering the education modules will be blinded to the in-office BP outcome measure unless a safety threshold is exceeded (systolic BP <90 or >180mmHg). BP may be re-checked separately as part of routine care.

Control participants will be encouraged to maintain participation in the study in order to minimize differential loss-to-follow-up between intervention and control group that would jeopardize the validity of study findings. As recommended by the design teams, we will conduct semi-annual participant engagement parties (in January and July) that will consist of a meal, healthy lifestyle education and games. We will report enrollment and other study related news to participants. All participants—both intervention and control—will be invited to these events. As an additional incentive, control participants will receive a BP monitor and instructions about its use after completion of the final 12-month trial visit.

EXTRA-CVD intervention: Participants randomized to the intervention will meet with the site prevention nurse on the day of enrollment. With nurse assistance, the participant will complete an initial ASCVD risk assessment using the ACC/AHA risk calculator and a risk visualization tool available at <https://statindecisionaid.mayoclinic.org/>. This exercise will help establish rapport between the participant and the nurse, and will help identify potential targets for intervention. The nurse will conduct a baseline medication assessment, including participant's knowledge of the purpose and side effects of each BP or cholesterol medication and current or potential adherence strategies.

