Frequency of contact: All subjects will complete the same assessments at the same time-points (in-office BPs, lipid profile, perceived ASCVD risk survey, and network analysis survey). The prevention nurse will then contact the intervention subjects at up to 2-week intervals as necessary to carry out the multi-component intervention. Frequency of contact will be determined according to protocol triggers that may be patient or prevention nurse initiated (e.g. home BP values are high, checking for side effects after starting a statin). At a minimum, the prevention nurse will have face-to-face meetings at 0, 4, 8, and 12 months, as well as a mid-period telephone call between in-person visits to “check-in” about home BP values and medication adherence. An initial 2-week follow-up call will ensure proper use of the home BP monitor and to address any other questions. Two example scenarios of relatively lower intensity and higher intensity intervention are shown in **Figure 3** with the education control group as a reference. As demonstrated by the figure, a strict attention control group is not appropriate since the dose of attention will vary according to the needs of the participant.

As with control patients above, study visits must be completed +/- 14 days from the calculated visit date. Visits done between 14 and 28 days after the calculated visit date will be considered a protocol deviation. Visits outside of the +28 day window will not be scheduled and that visit will be considered missing for that patient. The fasting lipid panel blood draw will be done at the time of study visit or within a +/- 10 day window. Study calls will be completed +/- 14 days of the scheduled due date. In the event that the study nurse has made no less than three

attempts to schedule a participant’s follow-up visit, a letter (Appendix R) will be sent to the participant.

[figure not shown]

Figure 3: Example scenarios of intervention participant contact frequency. (A) Participant with lower intensity requirements; (B) Participant with higher intensity requirement; (C) Control participant. Squares represent in-person visits and lines are telephone contact.

EXTRA-CVD Intervention components:

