1. Care coordination. Beginning with initial enrollment, the prevention nurse will coordinate blood pressure and cholesterol management for all participants in the intervention arm. Care coordination will consist of tailored discussions with the participant and his/her providers about which provider will take primary responsibility for BP and cholesterol management. Considerations of patient-provider trust and provider comfort level or experience will inform this decision. The prevention nurse will direct subsequent management decisions to the designated provider but will facilitate communication by notifying the non-designated of any changes to medications.

At the baseline visit, the prevention nurse will map the participant’s care team and communication preferences, to ensure that all providers in the patient’s care team are accounted for. After the initial visit, the nurse will contact members of the participant’s care team through normal clinical communication channels which are standard of care for that clinic site (e.g. EMR messages, email, phone) to inform them that the participant has been enrolled in the study. The prevention nurse may use this opportunity to discuss any potential modification to suggested blood pressure and cholesterol targets.

In order to better incorporate the prevention nurse into clinic workflow, a number of recommendations were made by the design teams. These include having nurse meet & greet and regular staff updates on the study to ensure that communication preferences are respected.

Component 1—Relevant process evaluation data for aim 3: (1) number and duration of telephone calls and emails to providers or providers’ staff; (2) number and nature of communication notes

in EMR; (3) prevention nurse trust & communication ties with providers; (4) time spent coordinating care.

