The primary outcome will be systolic BP at 12 months and secondary outcome will be non-HDL cholesterol at 12 months, both measured at 4 time-points (0, 4, 8, and 12 months). All BPs used for outcomes will be obtained by a blinded research assistant and cholesterol levels will be measured by lab personnel who are also blinded to treatment group. Because the outcomes are continuous, linear mixed-effects models⁸⁹ (LMM) will be used to examine the differences over time between the study arms. LMM will allow us to implicitly account for the correlation between a patient's repeated measurements over time. The general mean structure of the LMM we will use to examine the hypotheses is, $Y_{ij} = \beta_0 + \beta_1 * I(month = 4) + \beta_2 * I(month = 8) + \beta_3 * I(month = 12) + \beta_5 * arm * I(month = 4) + \beta_6 * arm * I(month = 8) + \beta_7 * arm * I(month12)$, where Y_{ij} represents the outcome of interest (i.e., SBP or non-HDL) for patient i at time j . In this model, we fit a common intercept and arm is the intervention group indicator. Similarly, time is classified, where for example, $I(month = 12)$ is a dummy variable equal to 1 for the 12 month time point. Random intercepts will be included for

each individual to account for correlation among repeated measurements over time. The primary analytic model will adjust for clinic site. The mixed effects model parameters will be estimated and tested using SAS PROC MIXED (SAS Institute, Cary, NC), and the hypothesis of between-arm differences over time will be tested using estimate statements within PROC MIXED. In particular, β_7 , the estimated difference in outcome between arms at 12 months, will be the primary effectiveness outcome assessed.

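### The ±10-day lipid window has no month-0 exception, so a baseline non-HDL value may be taken after randomisation and the first nurse session, which can understate the 12-month effect

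*Combined protocol and SAP*

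**What the plan says.** All references are to the protocol unless the SAP is named.

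- **Lipid time points (Aim 2 Procedures, Education control group).** Both arms have a "lipid profile (0, 4, 8, 12 months"), so month 0 is one of the four outcome panels.
- **Window (same section; repeated under Frequency of contact for the intervention arm).** "The fasting lipid panel blood draw will be done at the time of study visit or within a +/- 10 day window". Neither place treats the baseline visit differently.
- **Randomization.** "Participants will be randomized by RedCap at the time of their baseline visit".
- **EXTRA-CVD intervention.** "Participants randomized to the intervention will meet with the site prevention nurse on the day of enrollment". That session covers risk, current medication and adherence strategies. Under Care coordination: "Beginning with initial enrollment, the prevention nurse will coordinate blood pressure and cholesterol management for all participants in the intervention arm".
- **Informed consent.** For Aim 2, "then informed consent will be obtained at the baseline visit".
- **Model (Statistical Considerations; SAP, Primary analyses).** "In this model, we fit a common intercept and arm is the intervention group indicator". There is no arm main effect, so the arms share one month-0 mean.

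The Cholesterol paragraph has lipids checked at each in-person visit, but it does not say whether the draw comes before or after randomisation. The separate COVID-19 window of ±21 days is tied to target dates at 4, 8 and 12 months and does not bear on baseline.

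**The concern.** A baseline value should precede allocation. Here the allowance for timing falls on the wrong side of it. Because consent is taken at the baseline visit, a study-specific month-0 draw cannot use the minus half of the window; what remains is day 0 to day +10, after randomisation and, in one arm only, after nurse contact has begun. A fasting panel tied to a routine clinic visit is the kind of test that gets deferred.

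A model that sets the arms equal at month 0 reads any observed month-0 difference as chance and adjusts for it. If part of that difference is treatment effect, the adjustment removes some of the effect from the 12-month estimate. The outcome at stake is the secondary endpoint, non-HDL cholesterol. The exploratory lipids and the month-0 cholesterol cascade level, which the SAP scores from the measurement at that visit, use the same panel.

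**Working it through.** **Inputs (protocol, Power).** Non-HDL SD 41 mg/dL; within-person correlation ρ = 0.7; missingness 5%, 10% and 15% at 4, 8 and 12 months; two-sided α = 0.05. N = 300, allocated 1:1. Random intercepts imply an equal correlation between all visits.

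**Step 1. Reproduce the plan's figures.** I used the generalised least squares information matrix for the stated model (common intercept, month dummies, arm-by-month terms) with a normal approximation. With complete data, the variance of the month-12 effect is 4 × 41² × (1 − 0.7²)/300 = 11.43, so SE = 3.38. The stated dropout raises the SE to 3.63. Total N, computed against stated:

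| Power | 10 mg/dL | 15 mg/dL | 20 mg/dL |
|---|---|---|---|
| 70% | 244 / 248 | 110 / 110 | 62 / 64 |
| 80% | 310 / 310 | 138 / 148 | 78 / 80 |
| 90% | 416 / 424 | 186 / 184 | 104 / 104 |

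Eight of nine cells agree closely. The exception is 138 against 148; N = 148 gives 82.8% power, which is compatible with a search based on 1,000 simulations. At N = 300 and 15 mg/dL, power is Φ(15/3.63 − 1.96) = 98.5%, consistent with the plan's claim of more than 90%.

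**Step 2. Effect of a late baseline.** Let Δ be the true 12-month reduction, s the share of month-0 panels drawn late, and e the mean net early reduction (intervention beyond control) among those drawn late. The month-0 arm difference is then d0 = s × e. With a common month-0 mean, the model estimates the month-12 difference minus the slope of month 12 on month 0 times the month-0 difference. That slope is ρ, so

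estimated reduction = Δ − ρ × d0.

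The weight is 0.7 with or without the planned dropout. It runs from 0.5 to 0.8 if ρ does.

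**Step 3. Size for Δ = 15.** Both s and e are assumptions. Here e = 5 mg/dL and power = Φ(estimate/3.63 − 1.96).

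| s | d0 | Loss (0.7 × d0) | % of 15 | Estimate | Power |
|---|---|---|---|---|---|
| 5% | 0.25 | 0.175 | 1.2 | 14.825 | 98.3% |
| 10% | 0.50 | 0.35 | 2.3 | 14.65 | 98.1% |
| 25% | 1.25 | 0.875 | 5.8 | 14.125 | 97.3% |
| 50% | 2.50 | 1.75 | 11.7 | 13.25 | 95.5% |

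The smallest planned effect has less room. For a true 10 mg/dL, half the panels late with a quarter of the effect already present gives d0 = 0.5 × 2.5 = 1.25 and an estimate of 10 − 0.875 = 9.125. Power falls from 78.7% to 71.1%.

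**Step 4. Is the common intercept the cause?** If the month-0 means are left free and change from baseline is compared, the estimate is Δ − d0, a loss of 1.0 per 1 mg/dL. The common intercept reduces the loss to 0.7. Only a comparison of 12-month means without baseline would have none.

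**The case against.** **The window may have been written for follow-up visits.** Its sentence follows rules about calculated visit dates, and those dates are counted from the baseline visit, which has none of its own. The consent timing points the same way. This is a fair reading, but the wording covers any study visit, month 0 is a listed time point, and nothing else fixes the order. A site following the text may draw late.

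**Little can change in 10 days.** Much of this stands. The nurse recommends and the responsible provider decides on medication. The first scheduled contact comes after the window has closed: "An initial 2-week follow-up call will ensure proper use of the home BP monitor", among other purposes. Control participants also receive education at enrolment, so only the net difference counts. An early effect of 5 mg/dL is already one third of the 12-month target, and 10 mg/dL would be two thirds. A reader might infer losses of 1.75–3.5 mg/dL from the latter (25–50% late), with power near 89% at the top of that range: Φ(11.5/3.63 − 1.96). Nothing in the documents supports a change of that size so soon. Some early effect remains possible, because adherence support starts on day 0 and needs no new prescription.

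**The constraint of equal baselines is at fault.** A reader might infer this from the model, but Step 4 shows the reverse.

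**Conclusion.** The gap in the timing rule is real, and the direction of any bias is toward zero. The bias itself is conditional: it is zero unless non-HDL has already fallen more in the intervention arm by the time of a late draw. A reader might infer that the non-HDL result will be biased; the documents do not support that, since they report neither how many draws are late nor any early change. On the assumed 5 mg/dL, the loss is 1–2% of the target with few late draws and 6–12% with many. The 0.7 weight rests on the planning correlation and the random-intercept structure. The conclusion about the intervention would rarely change at 15 mg/dL. The primary systolic BP analysis is not affected by this window. The point merits a change because the remedy is simple, not because the expected damage is large.

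**What to change.** **Protocol.** State that the month-0 study panel is drawn after consent and before both REDCap randomisation and the nurse session. Record the date of every draw, with its order relative to randomisation when both fall on one day. Keep ±10 days for months 4, 8 and 12. A window of −10 to 0 days would not do, because it would allow a research draw before consent.

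**SAP.** Set month-0 panels drawn after randomisation to missing, by the same rule in both arms, at minimum as a sensitivity analysis, and report the share of late draws by arm. The mixed model keeps these participants through their follow-up values. Do not substitute medical-record panels in the primary analysis: the SAP's Missing data section restricts it to study-collected data, and the eligibility lipid value has no recency limit. If enrolment has closed, the rule still works wherever draw dates are on file. Leave the common intercept in place.

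**Cost.** A participant who is not fasting at the baseline visit would need another visit or would lack a baseline value. Setting late values to missing raises the 12-month SE from 3.63 to 3.69 at 10% late and 3.81 at 25%. At 25%, power for 15 mg/dL is Φ(15/3.81 − 1.96) = 97.6%, about the same as the 97.3% from keeping late values with a 5 mg/dL early effect. The gain is therefore an unbiased estimate rather than more power.

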We envision extending the HIV treatment cascade for two key CVD risk factors—blood pressure and cholesterol—to improve uptake of guideline-based ASCVD prevention therapies. **Step 1**, PLHIV should have their blood pressure and cholesterol screened, and abnormal values should be appropriately diagnosed as hypertension and hypercholesterolemia in the medical record; **Step 2**, those with hypertension or hypercholesterolemia should be prescribed appropriate guideline-based therapies; and **Step 3**, all should achieve guideline-based treatment goals. Developing the HIV treatment cascade for prevention of non-AIDS comorbidities is a logical downstream extension of the treatment cascade paradigm, just as the HIV prevention cascade is extending the treatment cascade further upstream¹⁹ (**Figure 1**).

[figure not shown]

Figure 1: The extended HIV treatment and prevention cascade

Blood pressure and cholesterol targets matter. To our knowledge, no HIV-specific blood pressure guidelines exist; however, international guidelines generally agree that treating to a target systolic blood pressure of 140mmHg for most patients is appropriate, while acknowledging that certain groups may merit more aggressive targets (e.g. <130 systolic for diabetes and chronic kidney disease)^{20,21}. The most recent AHA/ACC guidelines go further to recommend both pharmacologic and non-pharmacologic strategies to achieve a treatment target of <130mmHg for most patients²²; although these recent guidelines have yet to achieve widespread

Table 1: NLA treatment goals for PLHIV.

Risk Category	Criteria	NLA goal Non-HDL-C LDL-C
Low	N/A*	N/A*
Moderate	2 major risk factors (i.e. HIV + high BP only)	<130 mg/dl <100 mg/dl
High	≥ 3 major risk factors	<130 mg/dl <100 mg/dl
Very High	Known ASCVD OR Diabetes + ≥2 major risk factors *	<100 mg/dl <70 mg/dl

Major risk factors include: HIV, Age >45 men or >55 women, family history of early CAD, smoking, hypertension, low HDL-C.

* By design, all participants in our study will be > low risk and those with diabetes will be very high risk.

implementation. To achieve these targets, many will require more than one drug and a lifetime of titrating medication. Improving self-management is thus a critical component to successful treatment of blood pressure over time.²³

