Blood pressure. We will use an evidence-based blood pressure treatment algorithm (**Figure 4**, Tables and Figures uploaded separately) adapted from Kaiser Permanente and used in our prior studies.^{84,85} Once-daily medication and combination therapy will be recommended when possible. A follow-up a basic chemistry panel will be ordered when adding ACE/ARB, thiazide diuretic, or potassium-sparing diuretic. Medication up-titrations will be recommended at intervals of 2-4 weeks until control is achieved. Measures not shown in the figure will include but will not be limited to: (1) adding agents such as hydralazine, terazosin, clonidine; (2) considerations for comorbid kidney disease or prior ASCVD event; (3) avoiding combination use of heart rate slowing drugs.

Figure 4: Blood pressure treatment algorithm

Blood Pressure Algorithm

[figure not shown]

Other considerations

- Consider medication non-adherence
- Consider interfering agents (e.g. NSAIDs, excess alcohol)
- Consider white coat effect.
- Consider discontinuing Lisinopril/HCTZ and changing to chlorthalidone 25mg plus Lisinopril 40mg daily. Consider additional agents (hydralazine, terazosin, minoxidil)
- Avoid using clonidine, verapamil, or diltiazem together with a beta blocker. These heart rate-slowing drug combinations may cause symptomatic bradycardia over time
- Consider consultation with a hypertension specialist.

Figure 5A: Cholesterol treatment algorithm (part 1)

Cholesterol Algorithm

Risk Category	Criteria	Non-HDL Goal
Low-Moderate	• Most EXTRA-CVD patients	<130 mg/dl
High	• Known ASCVD • Diabetes + ≥2 major risk factors *	<100 mg/dl
Very High	• Multiple Major ASCVD events • 1 major ASCVD event + risk factors* (see below)	<100 mg/dl

Major ASCVD events

[figure not shown]
1. Recent acute coronary syndrome (<12 months)
2. History of MI or stroke (other than recent ACS above)
3. Symptomatic PAD (claudication with ABI <0.85, prior lower-extremity revascularization or amputation)

Risk Factors for Future ASCVD events

1. Age >65 years
2. Heterozygous Familial Hypercholesterolemia
3. History of prior CABG or PCI outside of the major events
4. Diabetes
5. CKD (eGFR 15-60 mL/min)
6. Current cigarette smoking
7. Congestive Heart Failure
8. Persistently elevated LDL >100mg/dL despite maximally tolerated statin therapy and ezetimibe

[figure not shown]
Protocol

Figure 5B: Cholesterol treatment algorithm (part 2)

Protocol

Figure 6: Protocol for management of statin associated muscle symptoms

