Cholesterol. We will use an algorithm (**Figure 5A-B**) adapted from National Lipid Association (NLA) guidelines for HIV-infected patients²⁵ and the 2018 ACC/AHA Guideline for the Management of Blood Cholesterol⁸¹. As a first step, the prevention nurse will determine the non-HDL target for each individual participant (Table 1; p. 7). For most participants in the trial, the target non-HDL will be <130mg/dL; however, high risk patients (such as those with history of prior ASCVD event) will have a more aggressive goal (<100mg/dL). As recommended by the guidelines, our algorithm will address drug-drug interactions with ART, including the safe use of higher dose statins (rosuvastatin and atorvastatin) if needed, when drug interactions are present. Lipid profiles (total cholesterol, triglycerides, HDL, LDL) will be checked at every in-person study visit. The nurse will have access to all cholesterol fractions, but the algorithm will focus on non-HDL as the primary target. When a new cholesterol medication is prescribed, the prevention nurse will call 2 weeks after initiation to discuss adherence and any possible side-effects. The nurse will use an evidence-based approach to evaluation and management of muscle symptoms and other intolerances of statins as recommended by NLA guidelines (**Figure 6**).^{82,83} This approach will include evaluation for other causes, drug-drug interactions, checking creatinine kinase levels, trial off statin, retriial of different statin, non-daily dosing of longer acting statin (i.e. rosuvastatin), and/or referral to a specialist.

Component 2—Relevant process evaluation data for aim 3: (1) frequency of BP and cholesterol algorithm use; (2) number of telephone contacts and total duration of time required to bring an elevated BP or cholesterol level under control; (3) Frequency of statin intolerance and proportion of intolerance cases ending in complete cessation of any statin; (4) Number of referrals to BP or cholesterol specialists.

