- 91 • Pregnant, breast-feeding, or planning a pregnancy during the study period
- 92 • Planning to move out of the area in the next 12 months
- 93 • Non-English Speaking

94 **Outcomes**

- 95 • **Primary:** 12-month change in systolic BP, calculated as the mean of two systolic BP readings
- 96 measured in the right arm, 1 minute apart.
- 97 • **Secondary:** 12-month change in non-HDL cholesterol, calculated as total cholesterol – HDL.
- 98 • **Tertiary:** change in the extended cascade categories for hypertension and hypercholesterolemia
- 99 ○ *Hypertension: 4-level category*
 - 100 ▪ Undiagnosed: hypertension is not listed on the EMR problem list
 - 101 ▪ Appropriately diagnosed: hypertension listed on the EMR problem list
 - 102 ▪ Appropriately managed: at least one medication prescribed for hypertension
 - 103 ▪ At treatment goal: <130 systolic
- 104 ○ *Hypercholesterolemia: 4-level category*
 - 105 ▪ Undiagnosed: hypercholesterolemia is not listed on the EMR problem list
 - 106 ▪ Appropriately diagnosed: hypercholesterolemia listed on the EMR problem list
 - 107 ▪ Appropriately managed: at least one medication prescribed for
 - 108 hypercholesterolemia
 - 109 ▪ At treatment goal, based on lifetime ASCVD risk
 - 110 - Low-moderate risk: <130 mg/dl
 - 111 - High: <100 mg/dl
 - 112 - Very high: <100 mg/dl
- 113 ○ Measured at each time point
 - 114 ▪ Diagnosis, management: EMR review by nurse
 - 115 ▪ At goal: measurement at that visit
- 116
- 117 • **Exploratory:** change in additional lipid measurements
 - 118 ○ Total cholesterol
 - 119 ○ Triglycerides
 - 120 ○ HDL
 - 121 ○ LDL
- 122

123 **Statistical Analysis**

124 ***Descriptive analyses***

125 Beginning with the chart review process, we will track ineligibility (number of patients, reasons),
126 declining to participate, and agreeing to participate but not proceeding to the initial visit. Once a patient
127 agrees to the phone screen, we will collect age, race, ethnicity, sex at birth, and gender. We will compare
128 demographics for those who enroll in the study to those who decline participation and to those who are
129 not eligible, using two sample t-tests (or nonparametric equivalent) and χ^2 tests. (*Table S1*)

130
131 We will further describe participating patients' characteristics (sociodemographic, lifestyle, medical
132 history). Continuous variables will be reported using mean (SD) or median (Q1, Q3) and categorical

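### The protocol's two non-HDL target tables give the label *High* different goals and print different risk-factor lists, and the SAP scores goal attainment by tier label without criteria

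*Combined protocol and SAP*

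**What the plan says.** **Protocol, section 8, Aim 2 Procedures, component 2, Cholesterol.** The algorithm is Figure 5A-B, "adapted from National Lipid Association (NLA) guidelines for HIV-infected patients" and from a later general cholesterol guideline. The next sentence points elsewhere for the target: "As a first step, the prevention nurse will determine the non-HDL target for each individual participant (Table 1; p. 7". The paragraph then says that most participants will have a goal below 130 mg/dL, but "high risk patients (such as those with history of prior ASCVD event) will have a more aggressive goal (<100mg/dL".

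**Protocol, section 2, Table 1.** *Moderate* (two major risk factors) and *High* (three or more) both have a non-HDL goal below 130. *Very High* (known ASCVD, or diabetes with at least two major risk factors) has a goal below 100. The factors are defined: "Major risk factors include: HIV, Age >45 men or >55 women, family history of early CAD, smoking, hypertension, low HDL-C". The asterisked note adds: "By design, all participants in our study will be > low risk and those with diabetes will be very high risk".

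**Protocol, Figure 5A.** *Low-Moderate*, described only as covering most trial patients, has a goal below 130. *High* (known ASCVD, or diabetes with at least two major risk factors, asterisked) has a goal below 100, as does *Very High*. One *Very High* criterion carries the same asterisk: "1 major ASCVD event + risk factors* (see below". The list printed below is headed "Risk Factors for Future ASCVD events". It contains age over 65, familial hypercholesterolaemia, prior revascularisation, diabetes, kidney disease, smoking, heart failure and persistently raised LDL. It does not contain HIV or hypertension.

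**SAP, Outcomes (tertiary).** The top level of the hypercholesterolaemia cascade uses Figure 5A's tier names and goals, for example "High: <100 mg/dl". Tiers are said to rest on lifetime ASCVD risk (a risk score, in the footnote to SAP Table 2). No cut-points or criteria are given.

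**The concern.** One paragraph relies on two sources for the same threshold. They attach different goals to one label and print different risk-factor lists.

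The threshold has two uses. In the intervention arm, a non-HDL value above goal brings in the nurse's medication management and adherence support. In both arms, the goal defines the highest level of the cholesterol cascade, which is tertiary in the SAP and in the protocol's Statistical Considerations, although the protocol synopsis lists it under secondary endpoints. If nurse and analyst work from different tables, a participant could be managed to one number and scored against another.

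**Working it through.** The plan states no figure for this point, so there is nothing to reproduce. The check compares the rules and then sizes the consequence for one affected participant.

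**Step 1: the rules side by side.**

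| Source | Goal <130 mg/dL | Goal <100 mg/dL | Printed risk factors |
|---|---|---|---|
| Table 1 | *Moderate*; *High* (≥3 factors) | *Very High*: ASCVD, or diabetes with ≥2 factors | Include HIV and hypertension |
| Figure 5A | *Low-Moderate* | *High*: ASCVD, or diabetes with ≥2 factors; *Very High* | Omit HIV and hypertension |
| SAP | *Low-moderate* | *High*; *Very high* | None given |

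**Step 2: criteria, with Figure 5A's major risk factors read as Table 1's.** Eligibility gives every participant HIV and hypertension, hence two Table 1 factors. I compared both tables over all combinations of known ASCVD (2), diabetes (2), sex (2), age 40, 50, 60 or 70 (4), and seven yes/no items: family history, smoking, low HDL-C, familial hypercholesterolaemia, kidney disease, heart failure and persistent LDL. That is 2 × 2 × 2 × 4 × 2⁷ = 4,096 profiles. Prior revascularisation was left out, on the assumption that it counts as known ASCVD. Profiles with different goals: **0**. The tier names move by one step and the numbers agree.

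**Step 3: criteria, with Figure 5A's asterisk read as its own printed list.** Goals now differ only for diabetes without ASCVD and with fewer than two listed factors: Table 1 gives <100 and Figure 5A gives <130.
- Diabetes not itself counted: for each age up to 65, 6 of the 32 combinations of the five remaining listed items have at most one present; at age 70, 1 of 32 has none. So 3 × 6 + 1 = 19, times 8 (sex, family history, low HDL-C) = **152** profiles.
- Diabetes counted as one listed factor: 3 × 1 × 8 = **24** profiles.
- Example under either count: age 50, HIV, hypertension and diabetes, non-smoker, no other listed factor.

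**Step 4: a Table 1 label carried into the SAP tiers.** This moves *High* participants with neither diabetes nor ASCVD from <130 to <100. Such participants without diabetes or ASCVD make up 1,024 profiles, of which 48 have only the two factors given by eligibility, leaving 1,024 − 48 = **976** profiles.

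Profile counts are logical combinations and say nothing about how common each is.

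**Step 5: how often the choice of goal changes at-goal status.** Inputs from the protocol's Power section: mean 132 mg/dL, SD 41, and a 15 mg/dL effect. Normality is my assumption.
- Mean 132: Φ((130 − 132)/41) − Φ((100 − 132)/41) = 0.481 − 0.218 = **0.263**.
- Mean 132 − 15 = 117: Φ(13/41) − Φ(−17/41) = 0.624 − 0.339 = **0.285**.

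So about 26 to 29% of *affected* participants would change status.

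**The case against.** The strongest reply is that this is a naming problem. Read by criteria, both tables send ASCVD and diabetes to <100 and everyone else to <130. The nurse is told to determine a target, which is a number; nothing instructs anyone to carry a Table 1 label forward. The SAP's tier names are Figure 5A's, and Table 1 has no *Low-Moderate* tier. The protocol's remark that high-risk patients have the lower goal, with most participants below 130, fits both tables.

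The asterisk can also be explained. The diabetes criterion in Figure 5A has the same wording as in Table 1, asterisk included, and only Table 1 defines major risk factors. The pointer to the list below is attached to a different row, and that list has a different heading and itself contains diabetes. Part of the figure is not in the text reviewed, so a footnote may exist. Targets are also advisory: the nurse may discuss modifying them with the care team, and the responsible provider makes the final decision.

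Most of this stands. It rules out the inference that every Table 1 *High* participant has two targets, and so any count of misclassified participants built on it. It does not remove the defect. The same asterisk marks both Figure 5A rows, and its only visible explanation leads to a list without HIV and hypertension. The SAP still scores by labels that differ in meaning from those in the table the nurse is sent to, and gives no rule for assigning them.

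**Conclusion.** The point holds as an unreconciled threshold with limited reach. *High* has two meanings across Table 1, Figure 5A and the SAP. Targets differ by criteria only for participants with diabetes, no ASCVD and fewer than two factors on Figure 5A's list, and only if the asterisk refers to that list. A mismatch by label arises only if a Table 1 label is carried into the SAP tiers.

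For an affected participant, the chance of changing at-goal status is about 26% at the planning baseline, assuming normality. The number affected cannot be derived, because the documents give no prevalence of diabetes or of the risk factors in the trial sample.

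The consequences are confined to the nurse's trigger in the intervention arm and the tertiary cholesterol cascade. A reader might infer that the primary result is at risk, or that sites are already working from different tables. The documents support neither: systolic BP and the continuous non-HDL outcome are defined without these tiers, and nothing describes differing site practice. The change is worth making because it costs little and removes a possible source of misclassification.

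**What to change.** Reconcile Table 1, Figure 5A, the Cholesterol paragraph and the SAP into one non-HDL target table with one risk-factor list, one meaning per label and a stated rule for assigning each tier. Say explicitly what the asterisk refers to. Which target applies to whom is for the investigators to decide. Cite only that table in the Cholesterol paragraph.

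Derive each participant's numeric target from it at baseline, in both arms, and have the SAP score goal attainment against that number instead of a tier label.

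The cost is protocol and SAP wording plus one derived baseline variable. Diabetes and prior ASCVD are already in the SAP's baseline table; confirm that any other factor on the reconciled list is collected in both arms. No new participants or procedures are needed.
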